3.2. Exclusion Criteria

- 3.2.1 Patients who have had chemotherapy or radiotherapy within 2 weeks of first dose of Zydelig.
- 3.2.2 Patients receiving any other investigational agents within 30 days of receiving Zydelig
- 3.2.3 Patients who were previously exposed to Zydelig and experienced progression of disease.
- 3.2.4 History of allergic reactions attributed to compounds of similar chemical or biologic composition to Zydelig.
- 3.2.5 Patients with active and/or untreated CNS lymphoma will not be eligible.
- 3.2.6 Patients with inflammatory bowel disease.
- 3.2.7 Uncontrolled intercurrent illness including, but not limited to ongoing or active infection (defined as requiring systemic antibiotic treatment and fever within 48 hours of screening), symptomatic congestive heart failure (patients with NYHA score of III and above are excluded), unstable angina pectoris, cardiac arrhythmia, or psychiatric illness/social situations that would limit compliance with study requirements.
- 3.2.8 Women who are pregnant or nursing or plan to become pregnant or nurse during the course of the study.
- 3.2.9 Positive HIV status.
- 3.2.10 Patients with lack of count recovery as defined by ANC > 500 cells/mm³, non-transfused platelet count > 20,000 K/mm³.
- 3.2.11 Patients who are unable to swallow pills.
- 3.2.12 Patients with moderate to severe lung disease including:
 - Patients requiring O₂ supplementation
 - Patients unable to walk 50 feet without stopping to rest
 - Obstructive lung disease as defined by pre-transplant FEV₁ ≤ 60% of predicted.
 - Restrictive lung disease as defined by pre-transplant FVC < 60% of predicted.
- 3.2.13 Patients taking strong CYP3A4 inhibitors or inducers with Risk X (Avoid Combination) according to Lexicomp. Please see appendix C for more information.
- 3.2.14 Patients with active hepatic disease, liver cirrhosis, or known HBV/HCV infection.
- 3.2.15 Patients with de novo diffuse large B-cell lymphoma.

3.2.16 Patients with h/o PCP pneumonia or positive CMV viremia confirmed twice at least 1 day apart at screening.

3.3 Inclusion of Women and Minorities

Both men and women, and members of all races and ethnic groups are eligible for this trial.

4. REGISTRATION PROCEDURES

All patients must sign the IRB approved informed consent. Human protection committee approval of this protocol and consent form is required. Patients must be registered with the Study Coordinator/Coordinating Center Contact, [name]. The following documents are to be submitted for review: signed informed consent, eligibility checklist completed and signed, all supporting documents that demonstrate eligibility requirements have been met such as lab results, pathology reports, medical history/progress note of Investigator. Please fax or email these documents to: [name], [contact], [contact]. Instructions concerning correlative/special studies will be conveyed at the time of registration. Upon review and verification of eligibility, an email or fax document will be sent to the registering center to confirm dose assignment.

5. TREATMENT PLAN

5.1 Zydelig Administration

Treatment will be orally administered on an inpatient and outpatient basis with the starting dose of 150 mg by mouth twice a day for continuous 28-day cycles. Treatment will continue until progression, intolerance, or patient/physician discretion to stop therapy. Zydelig will be started with count recovery (ANC over 500 cells/mm³, non-transfused platelet count over 20,000 K/mm³) in patients who are at least 30 days after induction and/or transplant but no more than 120 days post-transplant.

Reported adverse events and potential risks are described in Section 9. Appropriate dose modifications for Zydelig are described in Section 7. No investigational or commercial agents, or therapies other than those described below may be administered with the intent to treat the patient's malignancy.

Patients should swallow Zydelig tablets whole each morning and evening (i.e. every 12 hours). Tablets may be taken with or without food. Patients should keep track of adherence to Zydelig therapy by using the "Patients Drug Diary" (see appendix B). This diary will be collected at the end of each cycle. At the time of collection, the diary will be reviewed by a staff member and the patient will be prompted to complete any blank entries before completion of the visit. Should a patient miss or vomit a dose of Zydelig within less than 6 hours of the planned dose, the patient should take it as soon as possible. Patients who miss or vomit a dose of Zydelig longer than 6 hours after the planned dose should wait until the next scheduled dose to resume taking Zydelig.

5.2 General Concomitant Medication and Supportive Care Guidelines

Because there is a potential for interaction of Zydelig with other concomitantly administered drugs through the cytochrome P450 system, the case report form must capture the concurrent

use of all other drugs, over-the-counter medications, or alternative therapies. The Principal Investigator should be alerted if the patient is taking any agent known to affect or with the potential to affect selected CYP450 isoenzymes.

Agents typically used in the supportive care of patients undergoing treatment for NHL should not be manipulated due to potential drug interactions, unless toxicity is observed.

For management of skin toxicity (rash); i.e., topical emollients, topical steroids or keratolytic creams can be used.

Avoid concurrent use of Zydelig with other drugs that may cause liver toxicity.

For management of grade ≥ 2 pneumonitis, diarrhea, or hepatotoxicity, Zydelig needs to be held. Systemic corticosteroids can be started at the discretion of the investigator.

Recent reports showed increased risk of Pneumocystis pneumonia (PCP) and Cytomegalovirus infection (CMV) associated with Zydelig. Because of these known risks, Trimethoprim-sulfamethoxazole (TMP-SMX) will be given as one double-strength tablet daily or three times per week, or as one single-strength tablet once daily. For patients who cannot take TMP-SMX, we will offer dapsone 100 mg tablet once a day or atovaquone suspension 1500 mg once a day. Blood CMV PCR will be monitored once a month; no prophylaxis is required. PCP prophylaxis and CMV monitoring will start once the patient starts taking Zydelig and will end 1 month after stopping Zydelig. Patients will be taken off the study drug if they develop PCP pneumonia, if CMV PCR becomes detectable in the blood or they develop CMV infection.

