Idelalisib is a substrate for aldehyde oxidase, CYP3A, and UGT1A4 in vitro. Idelalisib inhibits CYP2C8, CYP2C19, CYP3A, and UGT1A1 and GS-563117 inhibits CYP2C8, CYP2C9, CYP2C19, CYP3A and UGT1A1 in vitro. Idelalisib and GS-563117 are not likely to inhibit CYP1A, CYP2B6, and CYP2D6. Idelalisib induces CYP2B6 and CYP3A4, but does not induce CYP1A2 in vitro. GS-563117 does not induce these enzymes. Idelalisib and GS-563117 are substrates of P-glycoprotein (P-gp) and BCRP in vitro. Idelalisib is not a substrate of OATP1B1, OATP1B3, OAT1, OAT3, or OCT2. GS-563117 is not a substrate of OATP1B1 or OATP1B3. Idelalisib inhibits P-gp, OATP1B1, and OATP1B3, and GS-563117 inhibits OATP1B1, OATP1B3 in vitro. Idelalisib is not likely to inhibit BCRP, OCT2, OAT1, or OAT3, and GS-563117 is not likely to inhibit P-gp, BCRP, OCT2, OAT1, or OAT3.

Effect of Other Drugs on Idelalisib

A single dose of 150 mg of Zydelig was administered alone and after rifampin (a strong CYP3A and P-gp inducer) 600 mg once daily for 8 days in healthy subjects. Rifampin decreased the geometric mean idelalisib AUC by 75% and the geometric mean C_{max} by 58%. Avoid coadministration of Zydelig with strong CYP3A and P-gp inducers. A single dose of 400 mg of Zydelig was administered alone and after ketoconazole (a strong CYP3A and P-gp inhibitor) 400 mg daily for 4 days in healthy subjects. Ketoconazole increased the geometric mean idelalisib AUC by 1.8-fold. No changes in the geometric mean C_{max} were observed. Patients taking concomitant CYP3A inhibitors should be monitored for signs of Zydelig toxicity

Effect of Idelalisib on Other Drugs

A single oral dose of midazolam 5 mg was administered alone and after Zydelig 150 mg for 15 doses in healthy subjects. The geometric mean midazolam C_{max} increased by 2.4-fold and the geometric mean midazolam AUC increased by 5.4-fold. Avoid coadministration of Zydelig with CYP3A substrates, as Zydelig is a strong CYP3A inhibitor. A single dose of 10 mg of rosuvastatin (OATP1B1 and OATP1B3 substrate) was administered alone and after Zydelig 150 mg for 12 doses in healthy subjects. No changes in exposure to rosuvastatin were observed. A single dose of 0.5 mg of digoxin (P-gp substrate) was administered alone and after Zydelig 150 mg for 19 doses in healthy subjects. No changes in exposure to digoxin were observed.

10.5 Toxicity.

Hepatotoxicity

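### Section 5.2 leaves supportive-care drugs unchanged until toxicity appears, while Section 10.4 says to avoid CYP3A substrates; neither rule is given precedence, and no other rule covers a drug that is only a substrate

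*Combined protocol and SAP*

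**What the plan says.** Section 5.2 requires the case report form to capture every concurrent drug, over-the-counter product and alternative therapy. It then gives two instructions on interactions. The first is an alert: "The Principal Investigator should be alerted if the patient is taking any agent known to affect", or with the potential to affect, selected CYP450 isoenzymes. The second is that supportive-care agents typical for NHL "should not be manipulated due to potential drug interactions, unless toxicity is observed".

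Section 10.4 treats three classes of drug differently:
- **Substrates:** "Avoid coadministration of Zydelig with CYP3A substrates, as Zydelig is a strong CYP3A inhibitor".
- **Strong inducers:** "Avoid coadministration of Zydelig with strong CYP3A and P-gp inducers".
- **Inhibitors:** "Patients taking concomitant CYP3A inhibitors should be monitored for signs of Zydelig toxicity".

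Exclusion 3.2.13 bars patients taking strong CYP3A4 inhibitors or inducers rated Risk X by Lexicomp, and refers to Appendix C for more information. Appendix C has a column of inhibitors, a column of inducers and a website address for further information.

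**The concern.** Avoidance is a rule applied before the drugs are combined. The 5.2 sentence allows a change only after harm has been seen. When a supportive drug is a CYP3A substrate, a site following 5.2 keeps the combination and waits for toxicity, and a site following 10.4 does not start it. Two sites could therefore act differently on the same patient while each follows a written instruction.

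The stake is mainly patient safety. There is also a link to the primary objective. Section 14 judges the drug by the proportion of patients removed for toxicity or intolerance, and toxicity from an avoidable combination could enter that count.

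**Working it through.** No formula applies and the plan states no figure to reproduce. The check sets the rules side by side for each class and asks whether any other provision settles the conflict.

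**1. A drug that is only a CYP3A substrate**
- 10.4: avoid, with no exception for supportive care.
- 5.2: leave alone unless toxicity is observed.
- 3.2.13: names inhibitors and inducers only, so it does not apply.
- 5.2 alert: covers agents that affect the isoenzymes. A pure substrate is acted on by the enzyme and, on the plain wording, is not covered. The alert also prescribes no action.
- Case report form: records the drug but does not prevent its use.
- Appendix C as printed: inhibitors 16 strong + 18 moderate + 2 weak + 8 other = 44; inducers 13; substrates 0.

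Result: the two instructions conflict and no other provision decides between them.

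**2. A strong CYP3A/P-gp inducer**
- 10.4: avoid.
- At entry: 3.2.13 applies, with Lexicomp Risk X as the grading source.
- Started on treatment: the 5.2 alert applies. However, 3.2.13 is worded as an entry criterion, and Section 5.3 allows up to one year or 12 cycles of treatment.
- The 5.2 toxicity trigger looks in the wrong direction, because an inducer lowers Zydelig exposure and that need not produce toxicity.

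Result: a small residual gap.

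**3. A CYP3A inhibitor**
- 10.4 asks only for monitoring, which is compatible with 5.2.

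Result: no conflict.

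**4. Size of the class effects reported in 10.4 (healthy subjects)**
- Substrate: "geometric mean midazolam AUC increased by 5.4-fold" and Cmax rose 2.4-fold. This is exposure to the other drug, not to Zydelig.
- Inducer: rifampin cut Zydelig AUC by 75% (100 − 75 = 25% left) and Cmax by 58% (100 − 58 = 42% left).

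**5. Is an affected supportive drug named?**
- 5.2 names four systemic supportive treatments: TMP-SMX, dapsone, atovaquone and corticosteroids.
- One of the four appears in Appendix C: corticosteroids, listed as glucocorticoids in the inducer column, with no strength given.
- Neither midazolam nor rifampin is described as a supportive-care drug.

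Result: none is shown, and no frequency is given, so no patient count can be calculated.

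**The case against.** The strongest reply is that Section 10 is drug background and Sections 5 to 7 govern conduct. The text differs elsewhere in the same way. Section 10.5 suggests considering PJP prophylaxis where 5.2 requires it. It allows Zydelig to resume after CMV resolves where 5.2 and Table 3 stop it. It permits liver tests every 1 to 3 months after six months where Table 1 keeps them every 4 weeks. On that view 5.2 simply prevails. The argument has some force, but the precedence is nowhere written. In all three examples the conduct section is the more cautious of the two, whereas here it is the less cautious. Section 5.2 also repeats the 10.5 instruction to avoid other hepatotoxic drugs, so it carries over some avoidance rules, and it gives no reason for leaving out the CYP3A ones.

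It can also be said that inducers are already handled and that 5.2 sensibly protects needed supportive care after transplant. Both points largely stand. They reduce the inducer part to a residual one, and they argue against mandatory prior approval with no exception for urgent care.

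A reader might infer more than the documents support:
- **That sites have no source for substrates.** The printed table has none, but a website is cited beside it, and its content cannot be checked here.
- **That Appendix C fails because its inducers are ungraded.** Section 3.2.13 gives that job to Lexicomp.
- **That corticosteroids prove a conflict.** Section 5.2 says "Systemic corticosteroids can be started at the discretion of the investigator", but their inducer strength is unstated, 10.4 bars only strong inducers, and Zydelig is held for the events that the steroids treat.

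**Conclusion.** The conflict is real for CYP3A substrates: two written rules give opposite instructions, with no stated order and no provision that reaches a drug that is only a substrate. For strong inducers only a minor gap on treatment remains. Inhibitors are not part of the point.

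Severity is minor. The conclusion rests on the plain wording of the alert and on reading 5.2 and 10.4 as both applying to sites. The 5.4-fold figure shows what can happen to one substrate and is not an estimate for this trial. It would be tempting to conclude that patients here are receiving such a drug, or that the primary toxicity result is biased. The documents name no affected drug in use and give no frequency, so neither conclusion is supported. The 34-patient sample size, the Type I error and the power are unaffected.

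**What to change.** 1. Add to the 5.2 sentence: *except agents that Section 10.4 says to avoid (CYP3A substrates, strong CYP3A/P-gp inducers), for which an alternative is used where one is available; otherwise the Principal Investigator is alerted and the patient is monitored, without delaying urgent care.*
2. Extend the Principal Investigator alert in 5.2 to CYP3A substrates.
3. State that the strong-inducer part of 3.2.13 continues while the patient takes Zydelig, with Lexicomp as the source.

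Inhibitors stay under the 10.4 monitoring rule, and Appendix C need not be rebuilt. This is a wording amendment. Its cost is some pharmacist queries and substitutions of supportive drugs; the number cannot be estimated, because the documents do not say how many such drugs are used. The change does not require holding Zydelig, so it does not by itself alter the average daily dose analysed under 14.3.

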5.3 Duration of Therapy

In the absence of treatment delays due to adverse events, treatment may continue for 1 year or 12 cycles (28 days per cycle) after transplant or until one of the following criteria applies:

- Disease Progression
- Intercurrent illness that prevents further administration of treatment
- Unacceptable adverse event(s)
- Evidence of PCP pneumonia or CMV viremia, confirmed at 2 consecutive blood draws at least 1 day apart with any value ≥ 500 IU/mL in plasma or evidence of documented CMV disease.
- Patient decides to withdraw from the study
- General or specific changes in the patient's condition render the patient unacceptable for further treatment in the judgment of the investigator.

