6. REQUIRED DATA/STUDY CALENDAR

Pre-Study Testing Intervals

To be completed within 16 DAYS before study treatment:

- All blood work
- History and physical

To be completed within 28 DAYS before study treatment:

- Any X-ray, scan of any type (e.g., CT or MRI) or ultrasound that is utilized for tumor measurement

To be completed within 42 DAYS before study treatment:

- Any X-ray, scan of any type (e.g., CT or MRI) or ultrasound that is not utilized for tumor measurement
- Bone marrow biopsy and aspirate (unilateral) is required if there washistory of bone marrow involvement.

	Prior to Treatment	Cycle 1 Day 1	Cycle 1 Day 8 ± 3 days	Cycle 1 Day 15 ± 3 days	Day 1 of Each Subsequent Cycle ± 3 days ^l	Cycle 2 Day 15 ± 3 days	Cycle 3 Day 15 ± 3 days	End of Treatment* * ± 3 days	Time of Restaging and Post-treatment Follow-up*, %
Tests & Observations									
History & Progress Note	X	X			X			X	X
Physical Examination	X	X			X			X	X ^j
Pulse, Blood Pressure	X	X			X			X	X
Height	X								
Weight	X	X			X			X	X
Performance Status	X	X			X			X	X
Drug Toxicity Assessment	X	X			X			X	
Solicited Abnormalities/AEs	X	X ^A			X ^A			X	
Laboratory Studies									
CBC, Diff, Platelets	X	X			X			X	X
Serum Creatinine, CrCl (est), BUN	X	X			X			X	X
Serum Electrolytes	X	X			X			X	X
AST, ALT, Alk Phos, Bilirubin	X	X		X	X ^A	X	X	X	X
Uric Acid, Phosphate, LDH	X	X			X			X	X
Blood CMV PCR	X	X			X			X	
Beta2-Microglobulin	X							X	

Serum or Urine BHCg	X ^B							X	
Thyroid Function Tests (T3,T4, TSH)	X ^E				X ^E			X	
Triglycerides	X ^I							X	
HIV~	X ^{C~}							X	
HBsAg~, Anti-HBc~Ab,HepC Ab~	X~							X	
ECG	X		X ^F					X	
Staging									
CT/MRI (chest/abd/pelvis) with Tumor Measurements	X							X	X ^D
CT Neck	X							X	X ^D
PET (or PET/CT)	X							X	X ^D
Bone Marrow Asp & Biopsy	X							X ^G	X ^G
Histologic Review	X							X ^K	
Correlative Samples	X ^H	X ^H						X ^H	X ^H

Table 1

* Restage every 3 cycles during treatment (i.e., cycles 3, 6, 9, 12, etc.), then every 3 months for 1 year, then every 6 months for another year.

** If off study prior to month 12 study treatment

% Starting at cycle 15 through cycle 24: Visit window +/- 4 weeks. Starting at cycle 27 through cycle 36: Visit window +/- 12 weeks.

^ Monitor ALT, AST, Alk Phos and bilirubin in all patients every 2 weeks (or 15 days) for the first 3 cycles of treatment, than every 4 weeks during subsequent cycles.

~ If done before the transplant, no need to repeat them.

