7. DOSING DELAYS/DOSE MODIFICATIONS

Please refer to table 2 below.

Patients who experience a Grade 2 or 3 toxicity and recover to \leq Grade 1 (or to pretreatment baseline level of toxicity) may continue treatment at the next lower dose level (i.e., Dose level 2 down to dose level 1).

Once the dose has been reduced, patients must remain at the reduced dose for 28 days. Dose escalation may occur at the discretion of the investigator and may occur every 28 days. Patients may have their dose de-escalated from level 2 to level 1, three times before being removed from treatment.

Please note:

- There are no dose escalations above 150 mg BID
- There are no dose reductions below 100 mg BID

Table 2

Dose Modification Schedule	
Dose Level	Dose of Zydelig
Level 2 (starting dose)	150 mg PO BID
Level 1	100 mg PO BID

Table 3

Dose Modifications for Toxicities Due to Zydelig

Pneumonitis	Any symptomatic pneumonitis		
	Discontinue Zydelig in patients with any severity of symptomatic pneumonitis		
ALT/AST	>3.0-5.0 x ULN	>5-20 x ULN	>20 x ULN
	Decrease Zydelig to 100 mg BID and monitor weekly until ≤ 1 x ULN.	Withhold Zydelig. Monitor at least weekly until ALT/AST are ≤ 1 x ULN, then may resume Zydelig at 100 mg BID.	Discontinue Zydelig permanently.
Bilirubin	>1.5-3 x ULN	>3-10 x ULN	>10 x ULN

	Decrease Zydelig to 100 mg BID. Monitor at least weekly until ≤ 1 x ULN.	Withhold Zydelig. Monitor at least weekly until bilirubin is ≤ 1 x ULN, then may resume Zydelig at 100 mg BID.	Discontinue Zydelig permanently.
Diarrhea*	Moderate diarrhea	Severe diarrhea or hospitalization	Life-threatening diarrhea
	Decrease Zydelig to 100 mg BID. Monitor at least weekly until resolved.	Withhold Zydelig. Monitor at least weekly until resolved, then may resume Zydelig at 100 mg BID.	Discontinue Zydelig permanently.
Neutropenia[^]	ANC 1.0 to <1.5 Gi/L	ANC 0.5 to <1.0 Gi/L	ANC <0.5 Gi/L
	Maintain Zydelig dose.	Decrease Zydelig to 100 mg BID. Monitor ANC at least weekly.	Interrupt Zydelig. Monitor ANC at least weekly until ANC ≥ 0.5 Gi/L, then may resume Zydelig at 100 mg BID.
Thrombocytopenia	Platelets 50 to <75 Gi/L	Platelets 25 to <50 Gi/L	Platelets <25 Gi/L
	Maintain Zydelig dose.	Decrease Zydelig to 100 mg BID Monitor platelet counts at least weekly.	Interrupt Zydelig. Monitor platelet count at least weekly. May resume Zydelig at 100 mg BID when platelets ≥ 25 Gi/L.

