Pneumocystis pneumonia	Any symptomatic pneumonia		
	Discontinue Zydelig in patients with any severity of PCP		
CMV viremia/infection	Any CMV viremia/infection		
	Discontinue Zydelig in patients with any CMV viremia/infection		
Abbreviations: ALT, alanine aminotransferase; AST, aspartate aminotransferase; BID, twice daily; PCP, pneumocystis pneumonia; CMV, cytomegalovirus; ULN, upper limit of normal			

*Moderate diarrhea: increase of 4–6 stools per day over baseline. Severe diarrhea: increase of ≥ 7 stools per day over baseline.

[^] G-CSF might be administered at the discretion of the investigator

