neutrophils decreased	78 (53)	20 (14)	16 (11)
hemoglobin decreased	41 (28)	3 (2)	0
platelets decreased	38 (26)	4 (3)	5 (3)

Grades were obtained per CTCAE version 4.03.

Serious Adverse Events Reported as Possibly, Probably, or Definitely Related to Zydelig

Table 6

System Organ Class	Adverse Event
Blood and lymphatic system disorders	Anemia Febrile neutropenia Neutropenia Red cell aplasia Thrombocytopenia
Gastrointestinal disorders	Colitis Diarrhea Ischemic colitis Nausea Esophagitis Stomatitis Vomiting

General disorders and administration site conditions	Fatigue Fever Influenza-like symptoms Pyrexia
Hepatobiliary disorders	Cholecystitis Cholecystitis, acalculous Cholecystitis, acute
Infections and infestations	Abscess Brain abscess Cellulitis Cytomegalovirus infection Endocarditis Herpes zoster Herpes zoster, ophthalmic Meningitis Pneumonia Pneumonia fungal Pneumonia, Pneumocystis jiroveci Sepsis
Hepatotoxicity	ALT increased AST increased Hepatic enzyme increased Transaminase increased
Metabolism and nutrition disorders	Anorexia Fluid retention Hypercalcemia Tumor lysis syndrome
Renal and urinary disorders	Renal failure Renal failure, acute
Respiratory, thoracic, and mediastinal disorders	Atelectasis Hypoxia Pneumonia, organizing Pneumonitis Pulmonary embolism Pulmonary fibrosis
Skin and subcutaneous tissue disorders	Rash Rash, generalized Rash maculopapular

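### Sections 5.2, 5.3 and Table 3 do not give one CMV stopping rule, and 5.2 and Table 3 differ on grade 2 diarrhea

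*Combined protocol and SAP*

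**What the plan says.** **CMV**

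- Section 5.2 takes patients off study drug for PCP, or "if CMV PCR becomes detectable in the blood or they develop CMV infection". It names no level and asks for no confirmation.
- The CMV row of Table 3 (section 7) reads "Discontinue Zydelig in patients with any CMV viremia/infection". It does not say what counts as viremia.
- Section 5.3 says that "treatment may continue for 1 year or 12 cycles (28 days per cycle) after transplant" unless a listed criterion applies. For CMV, the criterion is viremia "confirmed at 2 consecutive blood draws at least 1 day apart with any value ≥ 500 IU/mL in plasma", or documented CMV disease.
- On testing, 5.2 says "Blood CMV PCR will be monitored once a month; no prophylaxis is required". The study calendar (Table 1) places the on-treatment PCR at Cycle 1 Day 1 and then at "Day 1 of Each Subsequent Cycle ± 3 days". Neither schedules a repeat after a positive result.

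**Diarrhea and liver**

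- Section 5.2 requires the drug to be held for pneumonitis, diarrhea or hepatotoxicity of grade 2 or above.
- Table 3 reduces to 100 mg BID for moderate diarrhea, for ALT/AST above 3 and up to 5 x ULN, and for bilirubin above 1.5 and up to 3 x ULN. It withholds only in the next band.
- Section 5.1 points to section 7 for dose modifications.

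**Endpoint**

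- Section 14 judges the drug on the proportion not removed from study for toxicity or intolerance (0.70 satisfactory, 0.50 or less not). Section 14.1 reports the proportion removed for toxicity.

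**The concern.** Section 5.2 itself names CMV infection as a known risk of this drug and requires no CMV prophylaxis in these post-transplant patients. The monthly PCR and the action taken on it are therefore the main safeguard. If different sections attach different actions to the same result, sites can stop different patients, and some patients can stay on drug with viremia that another section treats as a reason to stop.

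There is also a link to the primary quantity. Table 3 is headed "Dose Modifications for Toxicities Due to Zydelig", and cytomegalovirus infection appears in Table 6, titled "Serious Adverse Events Reported as Possibly, Probably, or Definitely Related to Zydelig". Both suggest that a CMV stop would be counted as toxicity. If so, the rule a site follows can change the count on which the drug is judged.

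**Working it through.** The plan gives no computed figure on this point, so the check is a comparison of the rules, followed by simple arithmetic on timing and size.

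**1. CMV: the same result under each rule**

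| Result | Section 5.2 | Table 3 | Section 5.3 |
|---|---|---|---|
| One detectable PCR, unconfirmed | Stop | Stop, unless viremia means confirmed viremia | Not a listed CMV criterion |
| Two positive draws, all values below 500 IU/mL | Stop | Stop, unless viremia carries the 5.3 threshold | Not a listed CMV criterion |
| Two positive draws with a value of 500 IU/mL or more | Stop (already at the first) | Stop | Stop |
| Documented CMV disease | Stop | Stop | Stop |

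The rules agree on the last two rows. The gap is unconfirmed or low-level viremia, plus the wait for confirmation.

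**2. Time to confirmation under 5.3**

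Section 5.3 sets a minimum gap of 1 day between draws and no maximum. If a site waits for the next scheduled PCR:

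- nominal gap: one cycle = 28 days;
- each draw has a window of 3 days either way, so the range is 28 − 6 = 22 to 28 + 6 = 34 days.

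A site may also repeat the PCR the next day. The 22 to 34 days is what the schedule allows, not what it requires.

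**3. Diarrhea**

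Table 7 describes grade 2 as moderate, and Table 3 defines moderate diarrhea as 4 to 6 stools a day over baseline. So for grade 2 diarrhea, 5.2 holds and Table 3 reduces. This needs no outside source.

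How many patients could be affected, from Table 5 (N = 146, Zydelig monotherapy):

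- any grade 68, grade 3 or above 20, so 68 − 20 = 48 had worst grade 1 or 2;
- 48/146 = 32.9%; applied to 34 patients, 0.329 × 34 = 11.2.

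The split between grades 1 and 2 is not given, so patients at worst grade 2 number between 0 and about 11. The Table 5 diarrhea term also includes colitis, enterocolitis and gastrointestinal inflammation, and the rates come from patients treated for indolent lymphoma, not from post-transplant maintenance.

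**4. Liver**

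Whether the lowest ALT/AST and bilirubin bands in Table 3 are grade 2 depends on CTCAE laboratory cutoffs, which the protocol does not print. If they are grade 2, 5.2 (hold) and Table 3 (reduce) conflict. If they are grade 1, they do not.

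**5. Primary endpoint**

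Each additional removal counted as toxicity moves the observed proportion by 1/34 = 2.9 points, or 1/31 = 3.2 points on the 31 patients that section 14 uses for its precision figures. The number of additional removals needs a rate of low-level CMV positivity, and the protocol gives none.

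**The case against.** The best defence is that the rules can be reconciled. Section 5.3 is permissive: it says treatment may continue, not that it must, and it also lists unacceptable adverse events and investigator judgment as reasons to stop. A site that stops at the first positive PCR satisfies 5.2, 5.3 and Table 3 together. A reader might infer that 5.2 and 5.3 cannot both be followed; that is too strong. What remains is that, on this reading, the 500 IU/mL threshold has no effect, and nothing tells a site that the stricter section governs.

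A second defence is that Table 3 speaks of viremia, not of a detectable PCR. Section 5.3 and exclusion 3.2.16 both attach confirmation on two occasions to viremia, so Table 3 may carry that sense. It is therefore wrong to say that Table 3 plainly stops the drug for any detectable result. This stands, but Table 3 makes no cross-reference, and the detectable wording in 5.2 differs from 5.3 either way.

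Third, 5.1 sends the reader to section 7 for dose modifications, and 5.2 is a supportive care section. That favours the Table 3 action for diarrhea. It is a pointer and not an override, however, and the hold in 5.2 is worded as a requirement. The opening of section 7 also describes grade 2 or 3 patients recovering before they continue at the lower dose, which is closer to holding.

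Finally, section 10.5 advises interrupting for a positive CMV PCR until the infection resolves. It sits in the pharmaceutical information and reads as general drug advice, so little weight should rest on it as a competing trial rule.

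**Conclusion.** The point holds as an inconsistency between stated rules on a named safety risk, and it should be fixed. For unconfirmed or below-500 IU/mL viremia, 5.2 takes the patient off drug while 5.3 lets a site continue. Where confirmation is awaited, no maximum interval applies, and the next scheduled PCR is 22 to 34 days away. For grade 2 diarrhea, 5.2 and Table 3 give different actions, affecting between 0 and about 11 of 34 patients if the Table 5 rates carry over.

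Two stronger conclusions are not supported. A reader might infer that the CMV mismatch costs a definite amount of power or biases the primary result. The protocol gives no CMV positivity rate, and section 14 does not say whether a stop for asymptomatic viremia is removal for toxicity. The headings of Tables 3 and 6 only suggest it. All that can be stated is 2.9 points per extra counted removal. A reader might also take the hepatotoxicity mismatch as established; it is only probable, because the grade cutoffs are not printed. The diarrhea and liver mismatches are dosing and safety matters that reach the endpoint only indirectly.

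**What to change.** - State one CMV rule in identical words in 5.2, 5.3 and Table 3, with the clinical team choosing the threshold.
- If the 5.3 threshold is kept: interrupt Zydelig at the first detectable PCR, repeat the PCR within a fixed time such as 7 days, and discontinue permanently if viremia is confirmed at 500 IU/mL or more or CMV disease is documented. Say when the drug may resume otherwise.
- Replace the 5.2 hold sentence for diarrhea, and for consistency hepatotoxicity, with a reference to the Table 3 actions.
- Record CMV-triggered stops under their own reason code, and state in 14.1 whether they count as removal for toxicity. The Table 3 heading suggests that they do.

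The cost is amendment wording, one reason code, and at most one unscheduled repeat PCR per first positive result. Under the interrupt-and-repeat option, a patient whose first positive is not confirmed also has a short break in treatment. No extra patients or scheduled visits are needed.
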